Tumor Assessment	Bone scintigraphy	X				See Instructions			Section 8.1 and Section 10.3 Appendix 3	 Required for all patients (testing up to 45 days prior to C1D1 may be used for baseline assessment) Postbaseline bone scintigraphy should occur every 24 weeks (±4 days), with first assessment relative to Cycle 1 Day 1, until radiographic disease progression, death, start of a new anticancer therapy, or study completion, whichever occurs first Perform as scheduled, regardless of any treatment delays or interruptions Perform within 14 days of clinical progression Importantly, RECIST v1.1 emphasizes bone scintigraphy is not adequate to measure bone lesions; however, bone scintigraphy can be used to confirm the presence or disappearance of bone lesions A central radiology vendor will be used to collect and store images for BIRC review
Patient Diary (Arms A and C)			Х		X	Х				 Provide patient drug diary on Day 1 of each cycle for patients randomized to Arms A or C. Completed daily by patient Review at each study visit

	Study Period	Baseline	Stu	dy Treatmer	nt (Cycle =	28 days)		ontinuation ow-Up		
	Cycle	Screening	1 ai	1 and 2		4 and Beyond (if Applicable)	Short-Term Follow-Up ^a	Long-Term Follow-Up ^a		
	Visit	0	1,3	2, 4	5	6 and Beyond (if Applicable)	801	802–8XX		
	Relative Day within a Cycle	≤28	Day 1	Day 15° (± 3)	Day 1 (± 3)	Day 1 (± 3)	Day 30 (± 7)	(± 14)		
Procedure Category	Procedure								Protocol Reference	Instructions
Survival Information							Х	Х	Section 8.1 and Section 10.3 Appendix 3	 Survival information is collected during both study treatment and at post-discontinuation follow-up During long-term follow-up, survival information is collected approximately every 12 weeks (±14 days) for the duration of this period. Survival information may be collected in clinic or by contacting the patient or family directly (for example, via telephone). Long-term follow-up data collection may include post-discontinuation anticancer therapies. Date of progression on the FIRST post-discontinuation anticancer treatment should be collected.

	Study Period	Baseline	Stu	dy Treatmer	nt (Cycle =	28 days)		ontinuation ow-Up		
	Cycle	Screening	1 a	nd 2	3	4 and Beyond (if Applicable)	Short-Term Follow-Up ^a	Long-Term Follow-Up ^a		
	Visit	0	1,3	2, 4	5	6 and Beyond (if Applicable)	801	802–8XX		
	Relative Day within a Cycle	≤28	Day 1	Day 15° (± 3)	Day 1 (± 3)	Day 1 (± 3)	Day 30 (± 7)	(± 14)		
Procedure Category	Procedure								Protocol Reference	Instructions

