• To assess exploratory clinical parameters of Arm A compared to Arm B, and Arm C compared to Arm A	 Time to progressive bone metastases Time to first SRE (defined as either pathological fracture, spinal cord compression, radiation to the bone, or surgery to the bone) TTC CFS PFS2 (from randomization to disease progression on the next line of treatment or death) Time to worsening of ECOG PS of ≥2

Objectives	Endpoints
• To explore other PRO and HRQOL parameters of Arm A compared to Arm B, and Arm C compared to Arm A	 Time to worsening of physical function as measured by the physical function score of EORTC IL 19 Change from baseline as measured by EORTC QLQ- C30 and EQ-5D-5L Incidence of AE using the PRO-CTCAE item for diarrhea Change from baseline as measured by the PGIS- Cancer Symptoms
To compare clinical efficacy parameters of Arm C to Arm B	PFSOS
• To explore potential biomarkers related to the ER pathway and/or the pathogenesis of breast cancer	Biomarker results and efficacy outcomes

Abbreviations: AE = adverse event; BIRC = blinded Independent Review Committee; CBR = clinical benefit rate; CFS = chemotherapy-free survival; CTCAE = Common Terminology Criteria for Adverse Events; ctDNA = Circulating tumor DNA; DoR = duration of response; ECOG = Eastern Cooperative Oncology Group; EORTC IL 19 = European Organization for Research and Treatment of Cancer Item Library 19; EORTC QLQ-C30 = European Organization for Research and Treatment of Cancer Quality of Life Questionnaire-Core 30; EQ-5D-5L = 5-level-EuroQol; ER = estrogen receptor; HRQOL = Health Related Quality of Life; ITT = Intention to treat; NCI = National Cancer Institute; NRS = numeric rating scale; ORR = objective response rate; OS = overall survival; PFS = progression-free survival; PGIS = Patient's Global Impression of Symptoms; PK = pharmacokinetics; PROs = patient-reported outcomes; PS = performance status; SRE = skeletal-related event; TTC = time to chemotherapy.

4. Study Design

4.1. **Overall Design**

EMBER-3 is a Phase 3 global, randomized, open-label confirmatory study for patients with ER+, HER2- locally advanced (not amenable to curative treatment by surgery) or mBC, who have been treated with an AI, alone or in combination with a CDK4/6 inhibitor. Prior treatment with a CDK4/6 inhibitor is expected if this treatment is approved and reimbursed and the Sponsor may elect to limit the enrollment of participants who have NOT received prior treatment with a CDK4/6 inhibitor.

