8.1.2. Efficacy Assessments during Post-discontinuation Follow-Up

Post-discontinuation follow-up during the study period will be conducted as described in the SoA (Section 1.3). For those patients who are randomized and never receive study treatment or those who discontinue study treatment without objectively measured PD, the investigative sites will continue to monitor patients and periodically evaluate tumor response approximately every 8 weeks for the first 12 months with the first assessment relative to Cycle 1 Day 1 and thereafter approximately every 12 weeks by the same method used at baseline and throughout the study until the patient has objective disease progression, death, start of a new anticancer therapy or study completion. In addition, anticancer therapies initiated after study treatment discontinuation will be collected during this follow-up period.

After the patient has objective disease progression, radiologic imaging and photographic images are no longer required and the patient will be followed up approximately every 12 weeks until the patient's death or overall study completion. Lilly will continue to collect survival data on all patients but may reduce data collection for other efficacy data. Sponsor will notify investigators when this reduced data collection can begin.

Tumor assessments will be performed for each patient at the times shown in the SoA (Section 1.3).

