9.4.7. Other Analyses

9.4.7.1. Exploratory Analyses

All the exploratory analyses will be conducted for each comparison (Arm A versus Arm B in the ITT and the *ESR1*-mutation detected populations and Arm C versus Arm A in the ITT population) per the prespecified analysis populations, unless otherwise stated.

Time to progressive bone metastases is defined as the time from randomization to the date of earliest development of new bone metastases. Time to progressive bone metastases will be summarized for each treatment arm using the Kaplan-Meier method and will be compared between 2 arms using the log-rank test.

Time to first SRE is defined as the time from randomization to the first SRE event defined as either pathological fracture, spinal cord compression, radiation to the bone, or surgery to the bone. Time to first SRE will be summarized for each treatment arm using the Kaplan-Meier method and will be compared between 2 arms using the log-rank test.

Time to chemotherapy is defined as the time from randomization to the initiation of first postdiscontinuation chemotherapy. TTC will be summarized for each treatment arm using the Kaplan-Meier method and will be compared between 2 arms using the log-rank test.

Chemotherapy-free survival is defined as the time from randomization to the initiation of first postdiscontinuation chemotherapy or death, whichever is earlier. CFS will be summarized for each treatment arm using the Kaplan-Meier method and will be compared between 2 arms using the log-rank test.

Progression-free survival 2 is defined as the time from randomization to disease progression on the next line of treatment or death, whichever is earlier. PFS2 will be summarized for each treatment arm using the Kaplan-Meier method and will be compared between 2 arms using the log-rank test.

Time to worsening of ECOG PS of ≥ 2 is defined as the time from randomization to the date when ECOG PS score of ≥ 2 was observed for the first time. Time to worsening of ECOG PS of ≥ 2 will be summarized for each treatment arm using the Kaplan-Meier method and will be compared between 2 arms using the log-rank test.

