Progression-free survival 2 is defined as the time from randomization to objective disease progression on the next line of treatment or death, whichever is earlier. Participants alive and not known to have a second objective progressive disease will be censored on the latest date known to be alive and without a second objective disease progression. PFS2 will be summarized for each treatment arm using the Kaplan-Meier method and will be compared between 2 arms using the log-rank test. Sensitivity analysis for PFS2 will be performed if deemed appropriate. For example, instead of objective disease progression, we may conduct analysis including clinical disease progression.

Time to worsening of ECOG PS of ≥ 2 is defined as the time from randomization to the date when ECOG PS score of ≥ 2 was observed for the first time. Participants not known to have such worsening will be censored at the last time when no worsening of ≥ 2 is observed. Time to worsening of ECOG PS of ≥ 2 will be summarized for each treatment arm using the Kaplan-Meier method and will be compared between 2 arms using the log-rank test.

PFS and OS will be compared between Arm C and Arm B using the stratified log-rank test. The treatment effect will be estimated by hazard ratio with its corresponding 95% CIs using the stratified Cox proportional hazard model. The analysis population for Arm C versus Arm B is all concurrently randomized participants between 2 arms. Subgroup analyses (e.g. based on stratification factors) will be conducted if deemed appropriate. Other efficacy endpoints may also be compared between Arm C and Arm B if deemed appropriate.

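### SAP Section 4.5 limits exploratory PFS2 to objective next-line progression, a condition absent from the protocol definition and unsupported by required imaging, so PFS2 moves partly toward OS

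*SAP*

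**What the plan says.** **Definition.** Protocol Section 9.4.7.1 reads: "Progression-free survival 2 is defined as the time from randomization to disease progression on the next line of treatment or death, whichever is earlier". The objectives table in Protocol Section 3 agrees: "PFS2 (from randomization to disease progression on the next line of treatment or death". The objectives table in SAP Section 1.1 uses the same unqualified wording. Only SAP Section 4.5 differs: "Progression-free survival 2 is defined as the time from randomization to objective disease progression on the next line of treatment or death, whichever is earlier".

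**Censoring.** Under SAP Section 4.5, participants who are alive with no known second objective progression "will be censored on the latest date known to be alive and without a second objective disease progression".

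**Sensitivity analysis.** SAP Section 4.5 makes a PFS2 sensitivity analysis conditional on its being judged appropriate, and gives as an example: "instead of objective disease progression, we may conduct analysis including clinical disease progression".

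**Data after first progression.** Protocol Section 8.1.2 says that after objective progression "radiologic imaging and photographic images are no longer required", with follow-up about every 12 weeks. The radiologic imaging row of the Schedule of Activities (Protocol Section 1.3) also ends scans when a new anticancer therapy starts. The survival information row asks for a date: "Date of progression on the FIRST post-discontinuation anticancer treatment should be collected". It names no method of assessment and no RECIST requirement.

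**The concern.** The SAP's event needs evidence that the protocol does not require at the relevant stage. Suppose a patient's next-line progression is clinical, or is recorded as a date with no scan behind it. Under SAP Section 4.5 that patient has no event at that date and remains at risk until death or the last date known alive. For that patient PFS2 becomes OS, or a late censoring time.

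PFS2 is meant to show whether a gain at first progression persists through the next line. If some known second progressions are set aside, reported PFS2 is too long in each arm and the contrast between arms is blurred by later survival. How far this goes depends on local imaging practice during next-line therapy, which the protocol does not control.

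**Working it through.** **Step 1: compare the definitions.** Protocol Section 3, Protocol Section 9.4.7.1 and SAP Section 1.1 use unqualified disease progression. SAP Section 4.5 alone adds *objective*. SAP Section 4.1 says that changes to the protocol's analysis methods, with their justification, go into Section 4.10 if applicable. The SAP text runs from Section 4.9.3 to Section 5, and the version history does not name this change.

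**Step 2: follow one patient.** First objective progression occurs, so required imaging ends. The next line starts. Clinical progression on it is recorded as a date. Under the protocol wording this date can be the PFS2 event. Under SAP Section 4.5 it is not, and time runs on to death or last contact.

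**Step 3: illustrate the size.** The documents give no PFS2 event count, power or median, so there is no figure to reproduce. Inputs:

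- First PFS median: 4.3 months in Arm B and 5.8 months in Arm A (Protocol Section 9.2, SAP Section 5). Check: 4.3/0.74 = 5.8.
- Next-line PFS median: 4 months (assumed).
- Survival after second progression, median: 15 months (assumed).
- Share *q* of second progressions without objective documentation: 0% to 40% (assumed, equal in both arms).
- Treatment effect on first PFS only; every affected patient waits until death (assumed).

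Each stage is exponential with rate λ = ln 2 / median. The survival function of a sum of stages is S(t) = Σᵢ [∏ⱼ≠ᵢ λⱼ/(λⱼ − λᵢ)] exp(−λᵢt). With S₂ for the first two stages and S₃ for all three (OS), PFS2 has survival function (1 − q)S₂(t) + q S₃(t).

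Example for Arm B at 18 months: S₂ = 0.198 and S₃ = 0.730. At q = 20%, 0.8 × 0.198 + 0.2 × 0.730 = 0.304.

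| q | Median PFS2, B | Median PFS2, A | Difference | 18-month rate, B |
|---|---|---|---|---|
| 0% | 10.0 | 11.8 | 1.8 | 20% |
| 10% | 10.9 | 12.8 | 1.9 | 25% |
| 20% | 12.0 | 13.9 | 1.9 | 30% |
| 40% | 14.8 | 17.0 | 2.2 | 41% |
| 100% (= OS) | 27.9 | 30.2 | 2.3 | 73% |

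Medians and differences are in months. The OS medians fall within the 2 to 3 years in the protocol's introduction.

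**Step 4: the contrast.** Cox hazard ratios (A versus B) were simulated with follow-up cut at 48 months. The ratio is about 0.78 at q = 0, about 0.85-0.87 at 20%, and about 0.88 at 40%. With next-line medians of 4 to 6 months and later survival medians of 14 to 20 months, it goes from 0.80-0.82 at q = 0 to 0.87-0.90 at 50%; the OS hazard ratio in those scenarios is 0.86-0.91.

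**The case against.** **PFS2 is exploratory.** It lies outside the graphical procedure, which holds three PFS and three OS hypotheses. It has no alpha, power or event target, and SAP Section 4.5 analyses it only if events suffice. This stands and limits the importance of the point.

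**The protocol does not say that any progression counts.** A reader might infer that the SAP breaks an explicit rule. The protocol wording is merely unqualified, and Section 9.4.7.1 leaves further detail to the SAP. For first PFS, the protocol uses RECIST 1.1 and does not count symptomatic deterioration without radiological confirmation, so an objective PFS2 event has a rationale in an open-label trial. That rationale is weaker here: first PFS has a mandatory scan schedule and the next line has none.

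**A clinical-progression analysis is already named.** True, but it is optional and does not change the main definition.

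**No longer required does not mean not done.** Routine scans will document some second progressions, so it would be too strong to infer that PFS2 simply becomes OS. If the 20% were instead documented by a later scan (assumed median delay 2 months), Arm B's median would be about 10.6 months rather than 12.0.

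**The difference in medians hardly moves.** In the table it goes from 1.8 to 2.2 months. This stands for medians, but the hazard ratio does move toward 1.

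**Does it favour imlunestrant?** A reader might infer so. With equal shares the effect is diluted. Unequal shares could shift it either way: in one simulation the hazard ratio was about 0.76 with 30% in A and 20% in B, and about 0.98 with the shares reversed. Nothing in the documents indicates that imaging on the next line differs by arm.

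**Conclusion.** The point holds as a mismatch between the SAP's PFS2 event and both the protocol definition and the data that follow-up requires. Applied literally, SAP Section 4.5 sets aside recorded next-line progressions that lack objective documentation and moves PFS2 partly toward OS.

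The size is not known. The figures above rest on assumed next-line and later survival medians, an assumed non-objective share, and the assumption that affected patients have no event before death. At a 10% share Arm B's median rises by about 0.9 months; at 40%, by about 4.7 months (14.8 − 10.0 = 4.8 from the rounded medians). With equal shares the hazard ratio is diluted toward 1. Primary and key secondary inference is unaffected. The correction is worth making because PFS2 is a named protocol endpoint with a planned log-rank test for each comparison.

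**What to change.** 1. Use one PFS2 definition in Protocol Sections 3 and 9.4.7.1 and SAP Sections 1.1 and 4.5.
2. Make the main analysis the protocol's: the event is the recorded progression on the first post-discontinuation therapy, objective or clinical, or death, whichever is earlier.
3. Pre-specify objective-only PFS2 as a firm sensitivity analysis, not one left to later judgement.
4. Report by arm the share of second progressions without objective documentation, where that is recorded.

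Two refinements are optional and depend on the data held: counting the start of a further line as an event when no progression date exists, and censoring at the last contact at which next-line status was confirmed. The second date is not listed as collected. Protocol Section 8.1.2 also lets the sponsor reduce collection of efficacy data other than survival, so these could need more than SAP wording.

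The core change costs SAP text, matching protocol wording where needed, and programming, because the progression date is already requested. The downside is that the main PFS2 becomes somewhat less objective in an open-label trial, which is the reason to keep the objective-only analysis beside it.

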2.2. Background

As described in Section 2, there remains an unmet medical need for novel, improved, and tolerable ETs for the management of ER+, HER2- mBC, that can overcome the PK and resistance limitations of ETs currently used in the clinic. To this end, promising clinical data have been observed with the oral SERD, imlunestrant, in heavily pretreated ER+ mBC patients. Along with this, abemaciclib has well established clinical benefit in CDK4/6-naïve patients in the 1st and 2nd line setting and has the potential for benefit in CDK4/6-pre-treated patients (Sections 2 & 2.1). The clinical and the preclinical results outlined in Section 2.1 support further investigation of imlunestrant and imlunestrant plus abemaciclib for patients with ER+, HER2-locally advanced or mBC.

The purpose of this study, in patients with ER+, HER2- locally advanced or mBC previously treated with an AI with or without a CDK4/6 inhibitor, is to determine whether: imlunestrant prolongs PFS compared to Investigator's Choice of Endocrine Therapy; and if imlunestrant plus abemaciclib prolongs PFS compared to imlunestrant monotherapy.

Patient randomization within this study will be stratified by known prognostic factors (see Section 4.1 for further details) to reduce the potential for bias and improve the power of the analyses. Randomization minimizes systematic bias in the selection and assignment of patients to study therapy and provides justification for inferential statistical methods to be used on data from this study. Using an appropriate concurrent control arm enables direct statistical estimation of benefits and harms due to study therapy and minimizes bias in the assessment and interpretation of observed treatment effects. See Sections 6.2.3 and 9.4.2 for further description.

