6.3. Measures to Minimize Bias: Randomization and Blinding

This is a randomized, open-label study. The route of administration for the anti-cancer agents in the study justifies an open-label design. Upon obtaining informed consent, site personnel should

access the IWRS, which will assign a patient number. Participants who meet all criteria for enrollment will be randomly assigned to the treatment arm. Assignment to treatment groups will be determined by a computer-generated random sequence using the IWRS. Sites will be prompted to enter the specific Arm B ET of choice at time of randomization until the enrollment to Arm B is stopped. Each participant in this study will be aware of his or her own assigned treatment group. At each investigative site, all staff involved in treating and caring for study participants will have full knowledge of treatment assignments for the participants under their care.

In order to maintain the scientific integrity of the trial, access to study data will be strictly controlled prior to the interim and final analyses. Access to the EDC will be limited to those who require this information for their role and all access will be documented.

For the accumulated aggregate database to which Sponsor statisticians (or those of its designee) have access, treatment assignment, and other parameters that can disclose treatment assignment will be scrambled or masked. Therefore, the Sponsor and all investigative sites will remain blinded to treatment group assignments for the aggregate database until the database lock for the final analysis. Scrambled treatment assignments will be used in the reporting database until the study reaches its final analysis or the study is determined to be positive or futile by the DMC. During this time, analyses using unblinded treatment codes will be performed only at the interim analysis points specified in the protocol/SAP.

Participants will be randomized 1:1:1 between the 3 treatment arms, of either imlunestrant (Arm A), Investigator's Choice Endocrine Therapy (Arm B), or imlunestrant plus abemaciclib (Arm C), using the following stratification factors:

- previous treatment with any CDK4/6 inhibitor (yes versus no)
- presence of visceral metastases (yes versus no); visceral includes lung, liver, brain, pleural, and peritoneal involvement, and
- region (East Asia versus North America/Western Europe versus Others).

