1.2. Study Design

In the protocol amendment (a), participants will be randomized 1:1:1 between 3 treatment arms (Arm A: Arm B: Arm C) and will be treated until disease progression or other discontinuation criteria are met (Protocol Section 7).

- Arm A: Imlunestrant 400 mg orally QD on Days 1 to 28 of a 28-day cycle
- Arm B: Investigator's Choice Endocrine Therapy
 - Exemestane 25 mg orally QD on Days 1 to 28 of a 28-day cycle OR

- Fulvestrant 500 mg intramuscularly on Days 1 and 15 of Cycle 1, then on Day 1 of Cycle 2 and beyond
- Arm C: Imlunestrant + Abemaciclib
 - Imlunestrant 400 mg orally QD on Days 1 to 28 of a 28-day cycle
 - Abemaciclib 150 mg orally BID on Days 1 to 28 of a 28-day cycle

Arm C was added to the study (amendment a) after first patient visit for Arms A and B. All arms will be closed at the same time. Randomization of participants will continue in Arms A and B (1:1) until amendment (a) is approved and implemented, at which point participants will be randomized 1:1:1 (A:B:C) until the target enrollment for arms A and B (a total number of approximately 640 participants) is reached.

Investigator's Choice Endocrine Therapy (fulvestrant or exemestane) must be selected prior to randomization. Participants will be randomized using the following stratification factors:

- previous treatment with any CDK4/6 inhibitor (yes versus no)
- presence of visceral metastases (yes versus no); visceral includes lung, liver, brain, pleural, and peritoneal involvement, and
- region (East Asia versus North America/Western Europe versus Others).

The primary study objectives are to

- compare the PFS of Arm A to Arm B in the ITT population
- compare the PFS of Arm A to Arm B in the ESR1-mutation detected population, and
- compare the PFS of Arm C to Arm A in the ITT population.

The schema of the study is shown below.

Note: *ESR1*-mutation status will be centrally determined in plasma by Guardant 360 ctDNA assay from a blood draw at baseline.

Abbreviations: AI = aromatase inhibitor; CDK = cyclin-dependent kinase; ctDNA = Circulating tumor DNA; ER+ = estrogen receptor positive; FPV = first patient visit; HER2- = human epidermal growth factor receptor 2 negative; mTOR = mammalian target of rapamycin; n = number of participants; PI3K = phosphoinositide 3-kinase; PO = orally; QD = once daily; R = randomization; SERD = selective estrogen receptor degrader.

2. Statistical Hypotheses

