- ^d If there are multiple dates associated with 1 assessment, the assessment date will be set to the first date when the overall response is PD and the last date otherwise.

For the primary objective of PFS for Arm A versus Arm B in the ITT population, one interim PFS analysis will be conducted when approximately 192 (40% information fraction) investigator-assessed events have been observed in Arm A and Arm B, and the final PFS analysis will be conducted when approximately 480 investigator-assessed events have been observed in the same population. The interim analysis will allow the trial to stop early due to futility.

For the primary objective of PFS for Arm A versus Arm B in the *ESR1*-mutation detected population, the final analysis will be conducted when approximately 192 investigator-assessed events have been observed in the *ESR1*-mutation detected subset. The comparison of PFS curves

between treatment arms will be conducted by a stratified log-rank test as the primary analysis, stratified by the randomization strata, excluding region. Region is excluded in the stratified analysis for the subset to reduce the number of strata from 12 to 4. The treatment effect will be estimated by hazard ratio with its corresponding 95% CIs using the stratified Cox proportional hazard model with treatment as the only covariate. Similarly, region will be excluded in the stratified analysis.

For the primary objective of PFS for Arm C versus Arm A in the ITT population, 1 interim PFS analysis will be conducted when approximately 100 events have been observed among the approximately 440 participants concurrently randomized to Arm A and Arm C. This interim analysis will allow the trial (Arm A versus Arm C comparison) to stop early due to futility. The final analysis will be conducted when approximately 248 events have been observed among the participants concurrently randomized to both arms. The PFS between Arm C and Arm A will only be tested hierarchically based on the graphical approach.

See further details about the interim analyses in Section 4.9.3.

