4.4.1.2. Main Analytical Approach

OS curves, median OS, and OS rates at 1 year, 2 years, and 3 years with 95% CI for each treatment arm will be estimated using the Kaplan-Meier method. OS will be compared between treatment arms using a log-rank test stratified by the same factors as PFS, as the primary analysis for OS. The corresponding hazard ratio between treatment arms will be estimated using the stratified Cox regression model. The inferential analysis of OS will be based on the stratified analyses.

The analysis population for each OS comparison is the same as PFS. The OS endpoints will be hierarchically tested according to the graphical approach described in Section 4.3.3.

In the following subsection, we will present the boundary tables for H_4 , H_5 and H_6 for OS interim analyses assuming that H_1 , H_2 and H_3 are all rejected, intended to be illustrative only. The graph and the allocation of α for different OS endpoints will depend on the actual trial outcomes observed. The graph shown in Figure 4.5 displays the alpha level assigned to each endpoint under this scenario.

Figure 4.5. Graphical representation of testing scheme after H1, H2 and H3 are rejected.

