4.5. Exploratory Endpoints Analysis

All the exploratory analyses will be conducted for each comparison (Arm A versus Arm B and Arm C versus Arm A) per the prespecified analysis population for each comparison if the number of events is sufficient, unless otherwise stated.

Time to progressive bone metastases is defined as the time from randomization to the date of earliest development of new bone metastases or unequivocal progression of current bone lesions. Participants not known to have progressive bone metastases will be censored at the date of last documented tumor assessment. Time to progressive bone metastases will be summarized for each treatment arm using the Kaplan-Meier method and will be compared between 2 arms using the log-rank test.

Time to first skeletal-related event (SRE) is defined as the time from randomization to the first SRE defined as either pathological fracture, spinal cord compression, radiation to the bone, or surgery to the bone. Participants not known to have an SRE will be censored at the date of last documented assessment. Time to first SRE will be summarized for each treatment arm using the Kaplan-Meier method and will be compared between 2 arms using the log-rank test.

Time to chemotherapy (TTC) is defined as the time from randomization to the initiation of first post-discontinuation chemotherapy. Participants who die prior to the initiation of chemotherapy will be censored at the date of death. TTC will be summarized for each treatment arm using the Kaplan-Meier method and will be compared between 2 arms using the log-rank test.

Chemotherapy-free survival (CFS) is defined as the time from randomization to the initiation of first post-discontinuation chemotherapy or death, whichever is earlier. Participants not known to have initiated chemotherapy will be censored at the last documented assessment. CFS will be summarized for each treatment arm using the Kaplan-Meier method and will be compared between 2 arms using the log-rank test.

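### Six exploratory time-to-event endpoints get an unstratified log-rank test and no hazard ratio, although randomization is stratified; for frequent-event endpoints such as PFS2 this may cost some power.

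*SAP*

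**What the plan says.** Randomization is stratified. SAP 1.2 states: "Participants will be randomized using the following stratification factors", and lists prior CDK4/6 inhibitor (2 levels), visceral metastases (2) and region (3). Protocol 2.2 describes randomization as "stratified by known prognostic factors (see Section 4.1 for further details) to reduce the potential for bias and improve the power of the analyses".

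The test for OS follows that design. SAP 4.4.1.2: "OS will be compared between treatment arms using a log-rank test stratified by the same factors as PFS". PFS (SAP 4.3.2) and the two patient-reported time-to-event endpoints (SAP 4.6) also use the stratified test. In the *ESR1*-mutated subset, SAP 4.3.2 drops region "to reduce the number of strata from 12 to 4".

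SAP 4.5 does not follow it for six endpoints. For PFS2: "PFS2 will be summarized for each treatment arm using the Kaplan-Meier method and will be compared between 2 arms using the log-rank test". For chemotherapy-free survival (CFS): "CFS will be summarized for each treatment arm using the Kaplan-Meier method and will be compared between 2 arms using the log-rank test". Bone metastases, skeletal-related events, time to chemotherapy and ECOG worsening are handled in the same way, and Protocol 9.4.7.1 matches. None of the six has a specified hazard ratio or confidence interval. Yet the same SAP section says: "PFS and OS will be compared between Arm C and Arm B using the stratified log-rank test", and adds a stratified Cox hazard ratio for that comparison.

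**The concern.** When patients are balanced by design within prognostic groups, a test that ignores those groups uses a variance that is too large for the allocation. Its actual type I error then falls below the nominal level and it gives up power.

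Exploratory status does not explain the choice. Arm C versus Arm B and time to worsening of physical function are also exploratory, and both get the stratified test. No reason for the difference is given.

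At stake is efficiency and consistency for endpoints that will naturally be read beside PFS and OS, chiefly PFS2 and CFS. These would have no pre-stated effect measure and a possibly weaker test than their neighbours.

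**Working it through.** **1. Reproduce the plan's own power figures.** No event target or power is given for the six endpoints, so the PFS figures in SAP 5 serve as the anchor. One-sided log-rank power with 1:1 allocation is Φ(|ln HR|·√d/2 − z), with d events and z the normal quantile for 1 − α.

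- d = 480, HR 0.74, α = 0.025: 0.3011 × 10.954 = 3.298; 3.298 − 1.960 = 1.338; power 91.0% (plan: at least 91%).
- Same, α = 0.005: 3.298 − 2.576 = 0.722; 76.5% (plan: at least 76%).
- d = 192, HR 0.57, α = 0.02: 96.7% (plan: about 97%).
- d = 248, HR 0.70, α = 0.025: 80.2% (plan: at least 80%).

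All four reproduce.

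**2. Simulate the two tests.** From the documents: 12 strata (2 × 2 × 3), one-sided α = 0.025 (SAP 4.1), 640 patients for A versus B, 440 for C versus A, and the PFS hazard ratios for the frequent-event cases.

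Assumed, because the documents do not give them:
- permuted blocks of 4 within stratum (Protocol 6.3 says only "Assignment to treatment groups will be determined by a computer-generated random sequence using the IWRS");
- exponential times;
- prevalences of 60% (prior CDK4/6 inhibitor), 55% (visceral) and 30/35/35% (regions);
- prognostic hazard ratios for CDK4/6, visceral and per region step: weak 1.2/1.3/1.1, moderate 1.5/1.5/1.2, strong 2/2/1.4;
- the low-event counts and their hazard ratios.

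There were 10,000 trials per setting. Both tests were run on the same trials.

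Power in %, unstratified / stratified (gain from stratifying, in points):

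| Setting | Weak | Moderate | Strong |
|---|---|---|---|
| 640 pts, 480 events, HR 0.74 | 90.07 / 90.20 (0.13) | 89.41 / 90.97 (1.56) | 83.82 / 90.47 (6.65) |
| 440 pts, 246 events, HR 0.70 | 78.99 / 79.12 (0.13) | 77.50 / 78.92 (1.42) | 71.91 / 78.32 (6.41) |
| 640 pts, 64 events, HR 0.5 | 76.91 / 76.92 (0.01) | 76.34 / 76.67 (0.33) | 76.75 / 77.53 (0.78) |
| 640 pts, 32 events, HR 0.4 | 69.72 / 69.81 (0.09) | 69.20 / 69.36 (0.16) | 68.68 / 68.87 (0.19) |
| 440 pts, 26 events, HR 0.4 | 65.02 / 63.88 (−1.14) | 64.84 / 63.43 (−1.41) | 64.38 / 63.68 (−0.70) |

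Actual type I error of the unstratified test in %, nominal 2.5:

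| Setting | Weak | Moderate | Strong |
|---|---|---|---|
| 480 events | 2.60 | 2.31 | 1.51 |
| 246 events | 2.51 | 2.28 | 1.59 |

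The simulation error is √(0.025 × 0.975 / 10,000) = 0.16 points. The strong-factor values are therefore clearly below nominal, and the moderate ones only slightly so.

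**3. Checks on the assumptions.**
- A second simulation used the final OS event counts (SAP 4.4.1.3), prognostic hazard ratios of 1.5 or 2.0 for visceral disease and for prior CDK4/6 inhibitor, and 2,500 trials each. With 390 events and HR 0.78, stratified versus unstratified power was 70.0% versus 67.9% (gain 2.1) and 69.1% versus 62.6% (6.5). With 260 events and HR 0.75 it was 64.2% versus 62.5% (1.7) and 62.9% versus 57.0% (5.9).
- With no prognostic effect, in 2,000 trials, the unstratified test was slightly ahead: 91.15% versus 90.60% at 480 events and 80.30% versus 79.65% at 246.
- With simple randomization inside strata and strong factors, the unstratified type I error was 2.4% in 4,000 trials, so there was no clear conservatism.

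**4. Which endpoints have many events.** PFS2 and CFS both count death as an event. OS is planned to about 390 deaths (A versus B) and 260 (C versus A). If PFS2 and CFS are analysed at final OS, they should have roughly that many events or more. SAP 4.5 does not say when they are analysed, so this timing is an assumption.

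**The case against.** The strongest reply is that nothing turns on these tests. All six endpoints are exploratory, lie outside the graphical procedure, have no stated power, and are analysed only if events suffice. A plain log-rank test is valid here and errs on the safe side. That stands, and it sets the severity.

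Three stronger readings are tempting, and the documents do not support them.

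- *That all six tests lose power.* The size depends on prognostic strength and on balanced allocation within strata, neither of which the documents give. For endpoints with few events (possibly skeletal-related events or ECOG worsening) the 12 sparse strata cost the stratified test information, and the plain test can be slightly better.
- *That estimated effects are pulled toward no difference.* No hazard ratio is planned for these endpoints, so there is no specified estimate to attenuate.
- *That PFS2 and CFS cannot be compared with PFS and OS.* SAP 4.3.4 and 4.4.1.4 plan unstratified log-rank and Cox analyses of PFS and OS, and Protocol 9.4.3.2 also announces unstratified OS analyses. A like-for-like comparison of tests is available.

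It can also be said that the SAP never uses the word unstratified for these endpoints. But it writes stratified for Arm C versus Arm B in the same section, so reading the six as unstratified is fair. If stratification was intended, the text needs to say so.

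**Conclusion.** The point holds as a low-severity improvement. Six exploratory endpoints are compared by a test that ignores the design strata, with no effect measure and no stated reason, while the other time-to-event comparisons are stratified.

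For frequent-event endpoints, plausibly PFS2 and CFS, the cost in power is about 0.1 points with weak factors, 1.5 to 2 with moderate and 6 to 7 with strong ones. With about 26 to 64 events it is under 1 point or reversed by up to 1.4. These figures rest on assumed prognostic strengths, prevalences, blocked allocation and event counts. Type I error is not inflated, and no primary, key secondary or error-controlled conclusion changes.

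**What to change.** In SAP 4.5, and in Protocol 9.4.7.1 to match:

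- For PFS2, CFS and any other of the six with enough events, specify the stratified log-rank test and a stratified Cox hazard ratio with 95% CI. Use the PFS strata for each population, without region in the *ESR1*-mutated subset. Report the unstratified test as a sensitivity analysis.
- Where events are few, collapse strata (for example drop region, as SAP 4.3.2 already does for the subset) or keep the unstratified test. State in advance the event count that decides this.

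The cost is a few lines of wording, since the methods are already specified for PFS and OS. Protocol 9.4 lets a change that does not touch a principal feature be described and justified in the SAP and study report without an amendment.
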